## Trial registration

### Trial identifier and registry name

Clinicaltrials.gov: NCT05789095

### Protocol version

1.0, 23-Feb-2023

### Funding

No specific funding was provided for this study.

## Rationale and background

Osgood-Schlatter is an apophysitis of the tibial tubercle occurring in its primary form during adolescence. The condition affects one out of ten, and is even more prevalent in highly active adolescents.

Adolescents with Osgood-Schlatter experience a reduced ability to participate in sports and physical activities. A previous study from our group found that maximal strength and pain during isometric knee extension strength test on adolescents with Osgood-Schlatter, was moderately correlated to self-reported outcomes in terms of knee-related quality of life, sports participation satisfaction, mental health and pain beliefs. Rate of force development is a measure of explosive strength, or the ability to develop force over a short time period and is correlated to explosive actions, such as sprinting and jumping. In patients with prolonged or acute knee pain, rate of force has been found to be decreased. Several studies have shown that changes in rate of force development is linked to decreased neuromuscular function, and thereby is affecting sports function and activities of daily living. No previous investigations of rate of force development have been published for this group.

Measuring rate of force development in adolescents with Osgood-Schlatter, might further explain the relationship between features of knee function and self-reported outcomes. To account for differences in stature and bodyweight, normalizing for these variables will provide the more precise measure of rate of torque, often used in biomechanical research.

It would be interesting to investigate if rate of torque development is affected in this group. If it is, it could be explained by the theory that pain in local tissue, is affecting the ability to activate maximal muscle contraction in a limited time span. Furthermore, we suspect that the non-affected leg in the Osgood-Schlatter group, also will have a lower rate of torque development. This is based on the hypothesis that Osgood-Schlatter, affects the central nervous system due its chronicity, and therefore the ability to develop maximum rate of torque.

## Hypotheses

The hypotheses being tested are

1. that adolescents with Osgood-Schlatter, has a lower knee extension RTD in their affected knee compared to matched controls
2. that adolescents with Osgood-Schlatter, has a lower knee extension RTD in their affected knee compared to their potential asymptomatic knee
3. that adolescents with Osgood-Schlatter, has a lower knee extension RTD in their potential asymptomatic knee compared to matched controls
4. that adolescents with Osgood-Schlatter, has a lower knee flexion RTD in their affected knee compared to matched control
5. that adolescents with Osgood-Schlatter, has a lower knee flexion RTD in their affected knee compared to their potential asymptomatic knee
6. that adolescents with Osgood-Schlatter, has a lower knee flexion RTD in their potential asymptomatic knee compared to matched controls
7. That levels of either early or late rate of torque development is negatively correlated with pain during rate of torque development-testing, countermovement jump height or power, anterior knee pain provocation test score, current pain, pain duration, KOOS child 'Pain', 'Sport/rec' or 'QoL' subscales,

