## Methods

The study design and analysis strategy have been published along with a trial registration (ClinicalTrials.gov NCT05789095). The study will include 13 adolescent participants with Osgood-Schlatter and a group of 13 pain free controls matched on sex, age, and sports participation on the group level. Testing will include bilateral rate of torque development measurements of knee extension and flexion, with a fixated handheld dynamometer, during a single test-session lasting approximately two hours. The examiner responsible for strength-testing will be blinded to case-status. Along with anthropometric data, participants will perform the anterior knee pain provocation test to assess pain-response to sustained knee loading, a countermovement jump test to assess power and jump height, and provide patient-reported measures of condition severity, pain, disability, and quality of life. Data collection will start February 2023 and is expected to be completed by May 2023.

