### Statistical considerations

#### Sample size

No previous investigations of rate of torque have been published for adolescents with Osgood-Schlatter. One previous study using the same clinical test setup, equipment, and time-epochs (Early RTD: 0-100 ms, Late RTD: 0-200 ms, and peak RTD) for testing RTD over the hip in young (Under-19) professional soccer players found a mean of 9.57 Nm/kg/s and a standard deviation of 2.6 Nm/s/kg at 0-100 ms.

Considering that peak torque is around 30-50% lower for adolescents (U13 and U14) compared to U19 players, a similar difference might be expected for RTD, and thus we expect a group mean RTD of around 5 or 6 Nm/kg/s at 0-100 ms for asymptomatic adolescents. In adults with non-traumatic knee pain, investigations of RTD during maximal isometric hip extension, has shown differences between symptomatic participants and controls of >50 % during early RTD.

As this study includes RTD of the knee, which is the affected joint, we expect at least similar differences for our primary measure, early RTD at 0-100 ms, this would correspond for example to a between-group difference of 6 vs. 3 Nm/kg/s. We will assume 2.6 Nm/kg/s as an asymptomatic population standard deviation for 0-100 ms. Based on a two-sided two-sample t-test at 80% power and 5% alpha level, 13 participants in each group would thus be needed to detect a 50% between-group difference (R 4.0.2, Foundation for Statistical Computing, Vienna, Austria; RStudio 1.0.153, power.t.t.test package).

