## Statistical methods

The outcome variables (rate of torque development 0-100 ms, 0-200 ms, peak RTD, time to peak RTD, time to peak torque for both knee extension and knee flexion, respectively) will be compared between groups using an unpaired two-sided students t-test, assuming the residuals will be normally distributed, otherwise the non-parametric alternative, the Wilcoxon rank sum test, will be used. The alfa and beta-1 level will be set for 5% and 80%, respectively.

As outcome variables have been a priori specified and prioritized, and also analyzed and reported in the pre-specified order, no corrections for multiple testing will be applied. Data will be reported with between-group differences, standardized effect sizes based on Cohens d, exact p-values, and 95% confidence intervals. All data inspection, analysis, and visualizations will be conducted using R (R Foundation for Statistical Computing, Vienna, Austria), in the jamovi interface (The jamovi project 2023, version 2.4.1). All r-code and full data set will be shared with journal publication or in an open-access repository.

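### Hypothesis 7 is an either/or claim over at least 18 unranked correlations, and the plan's reason for not correcting for multiplicity does not reach it

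*Combined protocol and SAP*

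**What the plan says.** The Hypotheses section lists seven items as being tested. Items 1 to 6 each name a movement and a knee. Item 7 names neither. It reads "That levels of either early or late rate of torque development is negatively correlated with pain during rate of torque development-testing" and continues with "countermovement jump height or power, anterior knee pain provocation test score, current pain, pain duration, KOOS child 'Pain', 'Sport/rec' or 'QoL' subscales". It carries no exploratory label.

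The Sample size section defines the windows ("Early RTD: 0-100 ms, Late RTD: 0-200 ms, and peak RTD") and makes the 0-100 ms window the primary measure. The front summary under Methods says "Testing will include bilateral rate of torque development measurements of knee extension and flexion".

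In Statistical methods, the listed outcome variables (three RTD measures and two time-to-peak measures) "will be compared between groups using an unpaired two-sided students t-test". The error rates follow: "The alfa and beta-1 level will be set for 5% and 80%, respectively". On multiplicity the section says "no corrections for multiple testing will be applied", and its reason is "As outcome variables have been a priori specified and prioritized, and also analyzed and reported in the pre-specified order". It describes no correlation analysis: no coefficient, no analysis population and no criterion for hypothesis 7.

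**The concern.** The reason for not correcting is a ranking, and hypothesis 7 has none. The nine correlates are unranked, early and late RTD are offered as alternatives, and no leg or movement is chosen. Taken at its word, the hypothesis is satisfied by whichever pair happens to reach significance.

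The stake is what the paper may conclude. A single correlation with p<0.05 among 18 or more could be reported as support for a pre-specified hypothesis linking explosive strength to pain, jump performance or quality of life, when chance alone would often produce one.

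**Working it through.** **The plan's own figure.** The only computed figure is the sample size. A difference of 3 and SD of 2.6 Nm/kg/s, two-sided 5%, 80% power, two-sample t-test gives n = 12.83, so 13 per group, as stated. No error rate or power is given for hypothesis 7.

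**Count.** RTD windows: 2. Correlates: pain during RTD testing, jump height, jump power, provocation test score, current pain, pain duration and three KOOS-Child subscales, which is 9. So 2 x 9 = 18 pairs for one leg and one movement.

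**Independence benchmarks.** With k independent tests, P(at least one) = 1 - (1 - a)^k. A two-sided 5% test gives a = 0.05 for either sign and a = 0.025 for the negative sign only.
- k = 18: 1 - 0.95^18 = 0.60 either sign; 1 - 0.975^18 = 0.37 negative only.
- k = 9: 1 - 0.95^9 = 0.37 either sign; 1 - 0.975^9 = 0.20 negative only.

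**Allowing for correlation.** The two windows are nested and the correlates overlap in content, so the tests are not independent. The documents give no correlations, so I assumed ranges: 0.5 to 0.9 between early and late RTD, and a common value of 0 to 0.8 among the nine correlates. I simulated normal data with no RTD-correlate association, n = 13 (cases only, also an assumption), Pearson tests, 40,000 replicates per setting. The critical |r| is t/sqrt(n - 2 + t^2) with t = 2.201 on 11 df: 2.201/sqrt(11 + 4.844) = 0.553.

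| Tests | Early-late r | Correlate r | Negative only (nominal 0.025) | Either sign (nominal 0.05) |
|---|---|---|---|---|
| 18 | 0.5 | 0 | 0.35 | 0.59 |
| 18 | 0.5 | 0.5 | 0.24 | 0.46 |
| 18 | 0.8 | 0.5 | 0.21 | 0.41 |
| 18 | 0.9 | 0.5 | 0.19 | 0.37 |
| 18 | 0.9 | 0.8 | 0.12 | 0.24 |
| 9 (early only) | - | 0 | 0.20 to 0.21 | 0.37 |
| 9 (early only) | - | 0.5 | 0.14 | 0.28 |
| 9 (early only) | - | 0.8 | 0.09 | 0.18 |

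The negative-only column takes all nine correlates as positively related to one another. If pain-type and function-type measures instead run in opposite directions, the three middle 18-test rows rise to 0.30, 0.26 and 0.24 negative only.

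**Direction.** The hypothesis predicts a negative correlation throughout. The KOOS section makes 100 the optimal score, the Rationale ties explosive strength to jumping, and higher jump height and power are better performance. The stated direction therefore does not fit five of the nine correlates (jump height, jump power, three KOOS subscales). If the positive sign were accepted for those, which results count as support would change again.

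**The case against.** Several points on the other side stand.

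- **The success rule is inferred.** Nothing says that one significant pair makes hypothesis 7 supported; or may simply close a list of correlations to be reported separately. The 5% level and the no-correction sentence are written for the group comparisons and are carried over here only because nothing else governs. A reader might infer that the plan commits to claiming success on any hit; the documents do not say that. They leave it open.
- **The plan does rank early RTD first.** Imposing that on hypothesis 7 halves the count to 9. Outcome measures also names pain scores during force testing. But the nine correlates remain unranked among themselves, and the inflation is smaller, not gone.
- **Larger counts are not established.** Both movements would give 36 pairs, and both legs as well 72, but no section says that these enter hypothesis 7. The provocation test uses only one knee. Analysing all 26 participants is equally unspecified, and pain duration has no natural value in pain-free controls.
- **Correlations are not the main interest.** The Aim and Expected results sections concern group comparisons, the sample size does not depend on hypothesis 7, and exact p-values, confidence intervals and open data are promised. Fully reported, unadjusted secondary correlations are defensible. The Hypotheses section, however, does not call them secondary, and transparency does not settle what would count as support.

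**Conclusion.** The point holds: hypothesis 7 is a tested union of at least 18 unranked correlations, and the plan's ordering argument does not protect it.

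If any one significant pair counts, the chance of a false negative-direction finding with 13 cases is about 0.19 to 0.24 (0.12 to 0.35 over the assumed range), roughly 8 to 10 times the nominal 0.025 in the central settings. For either sign it is 0.37 to 0.46 (0.24 to 0.59), roughly 7 to 9 times 0.05. On the more favourable reading with early RTD only, it is 0.14 (0.09 to 0.21) and 0.28 (0.18 to 0.37).

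It would go too far to say that every setting exceeds five times the stated alpha. The lowest 18-test figure, 0.12, is 4.8 times 0.025 and only 2.4 times 0.05; the lowest 9-test figure, 0.09, is 3.6 and 1.8 times. The sizes rest on assumed correlations, normal data, Pearson tests, cases only and the inferred success rule. The case-control comparisons are not affected. It should be fixed because it decides whether an isolated correlation may be called a confirmed hypothesis.

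**What to change.** In Hypotheses, do one of two things:

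1. Move hypothesis 7 out of the tested hypotheses and label it exploratory. Report every correlation with its 95% CI, and make no claim that the hypothesis is supported on the strength of isolated p<0.05 results.
2. Name one confirmatory pair in advance, for example 0-100 ms knee extension RTD of the affected knee with NRS pain during that same test, in cases. Test only that pair at 5%, and label the rest exploratory.

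Either way, state the expected direction for each correlate, since a negative sign does not fit jump height, jump power or the KOOS scores. In Statistical methods, state that the pre-specified-order argument does not apply to hypothesis 7, and give the correlation coefficient and the analysis population.

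The cost is a few sentences and no new data. The downside is that isolated significant correlations can no longer be reported as confirmed hypotheses.

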## Background

Osgood-Schlatter is a growth-related condition involving multiple types of tissue in the tendon-bone interface at the tibial tubercle. Osgood-Schlatter affects one in ten adolescents causing persistent pain, reduced peak torque during knee extension, and reduced ability to maintain participation in sports and physical activity. Rate of torque development is linked to athletic performances, and reductions in rate of torque development is associated with decreased neuromuscular functioning and pain chronicity. As peak torque is reduced in Osgood-Schlatter, changes in rate of torque development is likely also affected, but this has not yet been investigated. This insight could help characterize the condition and guide management.

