#### Clinical examination and treatment

The study procedures will be conducted by two examiners (JL and HS). JL will be aware of the case status and conducts the screening and preliminary testing. To avoid bias, examiner HS will be blinded for the case status during trial and will not know the Numerical pain Rating Scale-scores (NRS, 0-10, 'no pain' to 'worst pain imaginable') of the participants during testing. To strengthen the inter-reliability, the examiners will not change roles during the study.

The session starts with JL examining the potential participant in the OSD-case group, for Osgood-Schlatter. If the Osgood-Schlatter diagnosis is made, the participant is then enrolled. For the potential participant in the control group, JL screens for potential injury or pain in relation to the knee joint. In the absence of relevant pathology, the control-participant is enrolled.

Then, JL measures length of the lever arm and variables for peak hight velocity assessment. Participants will then answer the patient-reported outcome measures together with their parent/guardian.

For the rate of force development tests, HS will enter the room and conduct the tests as described below. For each attempt the participant will write down their NRS-rating on a piece of paper, out of sight from HS.

Before the rate of force development test is conducted, the participants are told that they can always abort the test, if they perceive that pain rises to such a degree that they can't continue the

testing, or they start feeling fearful or uncertain of their symptoms. They are ultimately told that potential pain felt during testing are not harmful and will subside within 24 hours, as is our experience from multiple earlier conducted tests.

HS leaves the room, for JL to conduct the Anterior Knee Pain Provocation test and save the NRS results.

HS returns to conduct the Counter Movement Jump Test, again blinded for the participants NRS-scores, which are written down on a piece of paper. HS leaves the room, and JL either treats the patient (case-group) or hands out compensation for participating (control-group).

Cases and controls will be instructed not to take any pain medication 24 hours prior to any assessment to ensure that this does not affect measurements.

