#### KOOS

KOOS is used for patients with knee pain and injuries. The questionnaire contains questions within five categories: symptoms, pain, physical function in daily life, physical function during sports and activities, and life quality. In this study, participants will fill out questions from the ‘Sport/rec’ and

‘Quality of Life’ subscales, and questions P1, P4, P6a, and P6b from the ‘Pain’ subscale. Questions are answered on a 1-4likert scale in normalized to a 0-100 score for each subscale with 100 being the optimal score.

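### Hypothesis 7 puts one negative sign on all its correlates; that sign is reversed for the three KOOS-Child subscales and runs against the rationale for jump height

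*Combined protocol and SAP*

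**What the plan says.** Hypothesis 7, the last in the Hypotheses section, says that RTD is "negatively correlated with pain during rate of torque development-testing, countermovement jump height or power, anterior knee pain provocation test score", and the list goes on to "current pain, pain duration, KOOS child 'Pain', 'Sport/rec' or 'QoL' subscales". The sign is written once, at the head of the list. No second sign follows, and no other section restates or corrects the hypothesis.

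The scales are defined elsewhere. Under Clinical examination and treatment, pain is rated on a numerical scale: "NRS, 0-10, 'no pain' to 'worst pain imaginable". Under KOOS, answers are "normalized to a 0-100 score for each subscale with 100 being the optimal score".

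The premise is given in three places. The Background says that "reductions in rate of torque development is associated with decreased neuromuscular functioning and pain chronicity". The Rationale says "In patients with prolonged or acute knee pain, rate of force has been found to be decreased", and that "changes in rate of force development is linked to decreased neuromuscular function, and thereby is affecting sports function and activities of daily living".

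On jumping, the Rationale says that rate of force development "is correlated to explosive actions, such as sprinting and jumping". The Counter Movement Jump Test section treats a higher jump as better performance and records height in centimetres and power in watts. Under Outcome measures, RTD is divided by body weight.

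The Statistical methods section describes comparisons between groups. It gives no correlation analysis.

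**The concern.** The pain ratings and the KOOS-Child scores run in opposite directions: more pain raises the first and lowers the second. One sign cannot express the same idea for both. If lower RTD goes with more pain, its correlation with the pain rating is negative and its correlation with KOOS-Child Pain is positive.

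What is at stake is which results count as support for a hypothesis that the protocol lists among those being tested. Under the present wording, a negative correlation with a KOOS-Child subscale (faster torque development in adolescents who report worse status) would be read as support. A positive one, which is what the rationale leads one to expect, would not. If the intended direction is settled only after the coefficients are seen, this part of the plan is no longer pre-specified.

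**Working it through.** The plan gives no figure for hypothesis 7. Its one calculation, 13 per group, concerns the group difference in RTD at 0-100 ms: d = (6 − 3)/2.6 = 1.154, and a two-sided t-test at 5% and 80% power needs 12.83, rounded up to 13. It reproduces, and no correlation enters it.

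For hypothesis 7 the check is one of direction. The premise, from the Background and the Rationale, is that lower RTD goes with more pain and poorer function. Each correlate is then read against its own scale.

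| Correlate | A higher value means | Sign under the premise | Sign in hypothesis 7 |
|---|---|---|---|
| Pain during RTD testing | worse | negative | negative |
| Provocation test score | worse | negative | negative |
| Current pain | worse | negative | negative |
| Pain duration | worse | negative | negative |
| KOOS-Child Pain | better | positive | negative |
| KOOS-Child Sport/rec | better | positive | negative |
| KOOS-Child QoL | better | positive | negative |
| Jump height | better | positive, by inference | negative |
| Jump power (watts) | not settled | not fixed | negative |

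Count: 4 fit + 3 reversed + 1 contrary to the rationale + 1 open = 9.

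The support is not equally strong in every row.

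- **KOOS-Child Pain** is the clearest case. The same hypothesis gives the opposite prediction for pain measured on the rating scale.
- **Sport/rec** is supported by the Rationale's statement about sports function.
- **QoL** rests mainly on the general premise. The Rationale also cites a previous study in which maximal strength and pain during testing were moderately correlated with knee-related quality of life and satisfaction with sports participation. It gives no sign and concerns maximal strength, not RTD, so it does not settle the direction.
- **Jump height** rests on inference. The Rationale says only that the two are correlated, but it does so while describing a measure of explosive strength. The Background also links RTD to athletic performance.

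**Jump power.** Power is in watts, while RTD is per kilogram. Watts equal body mass times power per kilogram. On the log scale, with mass and power per kilogram taken as independent,

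r(RTD, watts) = (r_p × CV_p + r_m × CV_m) / √(CV_p² + CV_m²),

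where r_p and r_m are the correlations of RTD with power per kilogram and with mass. None of these inputs is in the documents. The assumed ranges are CV_m 0.1 to 0.3, CV_p 0.1 to 0.2, r_p 0.3 to 0.6 and r_m −0.5 to +0.3.

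- Lowest: (0.3 × 0.1 − 0.5 × 0.3)/√(0.01 + 0.09) = −0.12/0.316 = −0.38.
- Highest: (0.6 × 0.2 + 0.3 × 0.1)/√(0.04 + 0.01) = 0.15/0.224 = +0.67.

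Either sign is possible, so the negative sign for power cannot be called an error.

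**The case against.** The strongest reply is that little depends on the sign. Hypothesis 7 has no coefficient, analysis set, limb or threshold. It lies outside the stated aim and the sample size calculation, and any reader who knows that 100 is best on KOOS will interpret a coefficient correctly. This stands as an argument about weight, and it is why the point is minor. It does not make the written sign right.

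A second reply concerns the wording. The items are joined with *or*, so the hypothesis can be read as a list of alternatives. This also stands. A reader might infer that one positive KOOS-Child correlation would refute hypothesis 7. The text does not support that: such a result fails to support the hypothesis, and a negative correlation with another item could still support it.

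A third reply is that the authors meant loosely that lower RTD goes with worse status. That is probably so, but it is not what is written, and the scale definitions contradict the literal text.

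The sentence also ends on a comma, so it may be unfinished and the list may be longer than nine. The sign governing the KOOS-Child items stands before them, and the visible text gives no other.

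Finally, the documents write no positive sign for jumping. For jump height, the most that can be said is that the negative sign runs against the rationale.

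**Conclusion.** The concern holds in a limited form. The negative sign fits four of the nine correlates. It is reversed for the three KOOS-Child subscales, by their scoring together with the protocol's own premise. It runs against the stated rationale for jump height. For jump power no error is shown.

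The consequence is limited to how hypothesis 7 is interpreted. A correlation estimate, its confidence interval and its two-sided p-value do not depend on the predicted sign. Sample size, power and hypotheses 1 to 6 are untouched. This assumes that the correlations will be tested two-sided, as the group comparisons are; the plan mentions no one-sided test.

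A reader might want to express the error as a share of all tests, by multiplying correlates by time windows. That adds nothing, because the direction of a scale is the same in every window and the plan lists no set of correlation tests to serve as a denominator. No expected correlation is given either, so no probability of a wrong conclusion can be stated. The absence of a correlation method in the Statistical methods section is a separate matter, which correcting the signs does not resolve. Severity: minor.

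**What to change.** By dated amendment before analysis, restate hypothesis 7 with a sign for each correlate:

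- RTD negatively correlated with pain during RTD testing, provocation test score, current pain and pain duration;
- RTD positively correlated with KOOS-Child Pain, Sport/rec and QoL, and with countermovement jump height;
- jump power left without a direction unless a sign is justified, for example after expressing power per kilogram so that it matches the scaling of RTD.

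Each correlation is then read against its own stated sign. The cost is one amendment to one hypothesis, and a matching change to the published plan or registration if the hypothesis appears there. No participants, data or tests are added.
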